1.1. Introduction

Acute respiratory distress syndrome (ARDS) has a high mortality of 25~40%, even with the improvement of therapies. Previous studies suggest that prone positioning (PP) can increase the average ratio of arterial oxygen tension to the fraction of inspired oxygen ($\text{PaO}_2/\text{FiO}_2$) by +35 mmHg, and reduce mortality in moderate to severe ARDS, especially when combined with neuromuscular blocker (NMB) and low tidal volume ventilation, which decrease the risk of ventilator induced lung injury (VILI)¹⁻⁵. However, PP is only recommended in intubated severe ARDS with $\text{PaO}_2/\text{FiO}_2 < 150$ mmHg, and the use of PP is still limited in less than 33% of severe ARDS patients⁶.

From a theoretical and physiological point of view, HFNC may be beneficial in patients with ARDS. This techniques work via several mechanisms. Firstly, HFNC generates a small positive expiratory pressure. The amount of pressure generated depends on the nasal gas flow and whether the mouth is open or closed. HFNC works mainly by flushing the nasal airspaces, reducing anatomical dead space and providing a high FiO_2 . Secondly, HFNC is extremely well tolerated by delivering warm and well-humidified gas through the nostrils and avoiding the discomfort associated with wearing non-invasive ventilation (NIV) masks.⁷ Lastly, HFNC can provide constant F_1O_2 by avoiding air entrainment since the gas flow can be set to exceed most patient's inspiratory flow. The major goal of HFNC in treating ARDS is to achieve a sufficient level of oxygenation. However, HFNC may be viewed as a partial support therapy, but it is not totally addressing the underlying pathology of ARDS sufficiently, such as the ventilation-perfusion mismatching caused by alveolar collapse and consolidation in the dependent areas of the lung as this disease process worsens.⁸ In this regard, combination therapy such as PP with

HFNC may be considered to get better physiological effects by improving ventilation-perfusion mismatch in ARDS and a better homogeneity of lung mechanics.

The early application of PP with HFNC, especially in patients with moderate ARDS and baseline $SpO_2 > 95\%$, may help avoid intubation. In a preliminary study, PP was well tolerated with noninvasive respiratory supports, and the efficacy in terms of PaO_2/FiO_2 with HFNC + PP was higher than HFNC alone. Severe ARDS patients were not appropriate candidates for HFNC/NIV+PP, and a risk for delayed intubation should be noticed. A prospective RCT is warranted in the future in non-intubated moderate ARDS patients on the true benefits of PP before intubation.⁹

Coronavirus disease 2019 (COVID-19) is an emerging infectious disease that was first reported in Wuhan, China, and had subsequently spread worldwide, including in United States. Twenty-nine percent of COVID-19 patients may develop ARDS, 30% of these ARDS patients could be successfully supported with HFNC or NIV, and 60% of the ARDS patients needed intubation and invasive mechanical ventilation, or even ECMO support¹⁰.

Based on the potential beneficial mechanisms of HFNC and PP mentioned above, early use of PP combined with HFNC to avoid the need for intubation in COVID-19 patients with moderate to severe ARDS needs to be further investigated.

1.2. Hypothesis / Key Questions

We hypothesize that early use of PP combined with HFNC can avoid the need for intubation in moderate to severe ARDS patients. The purpose of this RCT will be to evaluate the effects of PP combined with HFNC for improving oxygenation and reducing the need for intubation

compared with HFNC support alone, as well as the safety of the PP therapy in non-intubated COVID-19 induced ARDS patients.

1.3. Primary Objectives

The primary outcome for the efficacy of PP combined with HFNC will be the treatment failure rate and intubation rate of HFNC or HFNC+PP support and clinical requirement for advanced respiratory support including NIV, invasive ventilation or ECMO.

1.4. Secondary Objectives

The secondary outcomes for the efficacy of PP combined with HFNC will be the improvement of SpO_2/FiO_2 or PaO_2/FiO_2 from HFNC alone to HFNC+PP. SpO_2/FiO_2 will be utilized to substitute PaO_2/FiO_2 as a means for evaluating oxygenation.¹¹⁻¹⁴ As a practical substitute to PaO_2/FiO_2 , SpO_2/FiO_2 has been shown to have a strong linear relationship in moderate to severe ARDS¹⁴ and was recommended as a diagnostic tool for early enrollment in clinical trial.¹³ F_iO_2 will be titrated to maintain SpO_2 at 90-95%. Other secondary outcomes including the time duration for PP therapy, patients' comfort with PP, PP complications including skin break down, tube/I.V. dislodgement, and the threshold of SpO_2/FiO_2 for successful PP in COVID-19 induced ARDS cases, HFNC duration, ICU length of stay and ICU mortality rate.

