3.2. Randomization and masking

Randomization will be stratified on ARDS severity (moderate and severe) performed by permuted block methods using Fisher and Yates tables of random permutations using a centralized interactive contact system is used for randomization. The random block length is 4, and random numbers are generated by computer. All of the centers participating in this study are immediately put in contact with the central unit (Rush University Medical Center) to obtain a randomization number if a patient fulfills the inclusion criteria. Within 6 hr of fulfilling inclusion criteria, a patient will be randomly allocated either to the prone positioning group or the control group (HFNC alone with no prone positioning therapy).

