3.8 Primary endpoint

28 days after randomization.

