4.2. Statistical analysis

Definition of the two groups: The patients who receive the prone positioning are classified as prone positioning group. The patients who receive HFNC alone are classified as HFNC group.

Comparisons between the two groups: Quantitative continuous variables are given as either means (\pm SDs) or medians (with inter-quartile ranges) are compared using the unpaired Student's t test or the Mann-Whitney test. Qualitative or categorical variables are compared with the chi-square test or the Fisher's exact test. ANOVA for paired tests to compare the same variables collected at different time points are used. The cumulative probability of remaining on spontaneous breathing are compared with the Kaplan-Meier estimate of survival and the log-rank test to compare the two groups. Univariate and multivariate analyses of risk factors for PP failure

are performed with logistic regression. All analyses are in intention to treat, and the level of significance is set at 0.05.

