4.3. Sample size calculation

Sample size estimation: Base on the intubation rate for COVID-19 induced ARDS patients reported in previous studies from 40% to 77%¹⁸⁻²⁰, we estimate at least a total of 346 subjects with an expected intubation rate of 60% in the moderate to severe ARDS patients with HFNC support, and of 45% [$80\% * (1-0.25)=45\%$, a 25% reduction] in the PP patients in our cases, with a confidence level $(1-\alpha)=95\%$ and power level $(1-\beta)=80\%$.

References

5. Kallet RH. A Comprehensive Review of Prone Position in ARDS. *Respir Care.* 2015;60(11):1660-1687.

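### Raw HFNC duration scores an early intubation like an early success, so effective prone positioning can appear to prolong HFNC; ICU stay lacks a rule for death.

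*Combined protocol and SAP*

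**What the plan says.** Section 1.4 of the combined protocol and SAP ends its list of secondary efficacy outcomes with "HFNC duration, ICU length of stay and ICU mortality rate". None of the three has a definition, a time horizon or a stated direction of benefit.

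Section 4.2 says that continuous variables "are compared using the unpaired Student's t test or the Mann-Whitney test". Categorical variables go to the chi-square or Fisher's exact test. Kaplan-Meier and log-rank methods are named only for remaining on spontaneous breathing. Analyses are by intention to treat. Nothing says how a patient who is intubated or dies counts in HFNC duration or ICU stay.

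Two other sections show that HFNC can stop for opposite reasons. Section 3.7 sets oxygenation thresholds for weaning. Section 3.8 (Treatment Failure Criteria) defines failure, which leads to NIV or intubation. Section 3.8 (Primary endpoint) gives only a time, "28 days after randomization", and gives it for the primary endpoint.

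**The concern.** A patient weaned on day 1 and a patient intubated on day 1 have the same HFNC duration. A rank or mean comparison of raw durations cannot tell them apart. The trial hopes to prevent intubation. If it does, some patients move from the group whose HFNC is cut short by failure to the group that stays on HFNC until weaning. Raw HFNC time then rises in the PP arm because the treatment works. A reader who takes shorter as better would see a disadvantage. A reader who takes longer as better would credit slow weaning. The test has no clear meaning either way.

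ICU stay shares the problem only through death: an early death is recorded as a short stay, and no rule corrects for it. At stake is the reading of two named secondary outcomes, not the primary result.

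**Working it through.** **Inputs from the plan.** Intubation 60% on HFNC alone and 45% with PP, total 346, power 80% (section 4.3); "the level of significance is set at 0.05" (section 4.2). Two-sided testing and 1:1 allocation are not stated. They are assumed, and the reproduced sample size supports them.

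**Reproducing the sample size.** With pooled variance and no continuity correction:

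n per arm = [1.960 × √(2 × 0.525 × 0.475) + 0.842 × √(0.60 × 0.40 + 0.45 × 0.55)]² / 0.15² = 172.8, so 173 per arm and 346 in total.

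This matches the plan. (The bracket in section 4.3 prints 80% × (1 − 0.25) = 45%. But 80% × 0.75 = 60%, whereas 60% × 0.75 = 45%. It reads as a misprint, and the rates used are 60% and 45%.)

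**HFNC duration, mean.** Let S and F be the mean durations in successes and failures, taken as equal in both arms.

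- HFNC alone: 0.60F + 0.40S
- PP: 0.45F + 0.55S
- Difference, PP minus HFNC alone: 0.15 × (S − F)

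The documents give no durations, so S and F are assumptions. With F = 2 and S = 6 days, the means are 3.6 and 4.2 days, a difference of +0.6. With F from 1 to 3 and S from 4 to 10 days, the difference runs from 0.15 × (4 − 3) = +0.15 to 0.15 × (10 − 1) = +1.35 days. With S = F it is zero.

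**HFNC duration, Mann-Whitney.** Simulated trials with 173 per arm, failure times exponential, success times gamma (shape 4, median 5 days), same durations in both arms unless stated:

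| Failure median (days) | HFNC significantly longer with PP |
|---|---|
| 1 | about 57% |
| 1.5 | about 43% |
| 2 | about 30% |
| 3 | about 13% |
| 4 | about 4% |
| 1.5, and PP shortens successful HFNC by 20% | about 4% |

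Repeat runs differ by up to about three percentage points. In the 1.5-day case the median HFNC time is 2.8 days on HFNC alone and 3.5 days with PP, and PP is significantly shorter in almost no trial. With equal medians, each direction is significant in about 2.5% of trials, as chance would give.

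**Support-free days on the same scenario.** In the 1.5-day case, assume also that 40% of failures die and that ventilation lasts a median of 12 days. Days alive and free of support to day 28 (0 if dead) then favour PP significantly in about 60% of trials and never favour HFNC alone. Across the other assumption sets tried, the figure is 46% to 66%.

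**ICU stay.** Assume that non-intubated patients stay 8 days if they survive, and that 5% of them die, at 5 days. Their mean is 0.95 × 8 + 0.05 × 5 = 7.85 days. The difference, PP minus HFNC alone, is 0.15 × (7.85 − mean stay if intubated).

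- 80% of intubated patients die, at 4 days, and survivors stay 10: mean 5.2, difference +0.40 day.
- 40% die, at 14 days, and survivors stay 20: mean 17.6, difference −1.46 days.

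Of 36 such scenarios, 30 give a shorter mean stay with PP. The six that give a longer one all have deaths at 4 or 7 days. If PP instead only lowers mortality from 40% to 30% (assumed), the difference is 0.10 × (stay of survivors − stay of those who die). That is 0 to +1.0 day for deaths at 5 to 10 days and survivor stays of 10 to 15 days.

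**ICU mortality.** With 40%, 60% or 80% mortality if intubated (assumed), mortality is 24% v 18%, 36% v 27% or 48% v 36%. PP is better in each case.

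**The case against.** A reader might infer that all three outcomes are biased against an effective treatment because intubation and death shorten stays. The documents do not support that. Intubation does not end an ICU stay and normally lengthens it, so raw ICU stay usually still favours PP. A reversal needs many and early deaths. ICU mortality is a binary count under intention to treat, and truncation cannot turn it round. Its only weakness here is the missing time point.

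For HFNC duration, the strongest reply is that the size depends on durations the plan does not give. It fades when failures leave HFNC late, or when PP also speeds weaning: with a failure median of 3 days and successful HFNC 20% shorter under PP, one run found PP longer in 0.1% of trials and shorter in 12%. That stands, and no single percentage should be quoted as the expected error.

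Nor does the plan say that longer HFNC is worse, so a reading as harm is an inference. The outcome would also be read beside the primary failure outcome and the analysis of time on spontaneous breathing, which limits misreading. But this does not give the raw comparison a meaning of its own.

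Finally, it is tempting to call the change a matter of wording because patients are followed to day 28. The plan states that time for the primary endpoint only.

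**Conclusion.** The point holds for HFNC duration. The planned test mixes two opposite reasons for stopping. If failures leave HFNC sooner on average than successes, and durations are otherwise equal in the arms, a treatment that prevents intubation lengthens mean raw HFNC time. On the assumed durations, a significant result in that direction occurs in anything from about 4% to 57% of trials. The direction of the mean follows from the plan's own 60% and 45%; the size rests on assumption.

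For ICU stay the point is smaller: death truncates the stay without a rule and can mask a benefit, but raw stay will usually still favour PP. For ICU mortality there is no such distortion, only a missing fixed time point. All of this concerns secondary outcomes. The primary outcome and the total of 346 are unaffected.

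**What to change.** Amend sections 1.4 and 4.2 before the data are unblinded:

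- Replace the between-arm test of raw HFNC duration by days alive and free of HFNC and advanced respiratory support (NIV, invasive ventilation or ECMO) to day 28, scored 0 if the patient has died, compared by Mann-Whitney.
- Replace ICU length of stay by ICU-free days to day 28, scored 0 if dead, compared in the same way.
- Report raw HFNC duration and raw ICU stay descriptively, split by outcome (weaned or failed; alive or dead).
- Report mortality at day 28.

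Cumulative incidence with competing events would be a workable alternative for the two durations.

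**Cost.** No more patients are needed. The composite scale is less intuitive than days on HFNC or days in the ICU. The sponsor must also confirm that start and stop dates of each form of support, ICU dates and vital status are recorded to day 28 for every patient, including after discharge. Section 4.1 mentions treatment and outcome only in general terms. If these items are not collected, the change needs additional data collection as well as new wording.

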2. STUDY METHODS

This is a multi-center randomized controlled trial, which will be approved by the Ethic Committees of all the participant hospitals. This trial is registered with ClinicalTrials.gov (NCT04325906).

2.1. Inclusion criteria

The diagnostic criteria for COVID-19 pneumonia will be based on the CDC guidelines. The diagnosis of ARDS will be assigned to patients who meet the Berlin definition criteria ¹⁵:

- 1) Presence of acute hypoxemic respiratory failure;
- 2) Acute onset within 7 days of insult, or new (within 7 days) or worsening respiratory symptoms;
- 3) Bilateral opacities on chest x-ray or CT not fully explained by effusions, lobar or lung collapse, or nodules;
- 4) Cardiac failure not the primary cause of acute respiratory failure.

Patients are categorized into 2 mutually exclusive classes of ARDS severity using previous definitions based on degree of hypoxemia:

- 1) Moderate: $100\text{mmHg} \leq \text{PaO}_2/\text{F}_1\text{O}_2 < 200\text{mmHg}$, or $140 \leq \text{SpO}_2/\text{F}_1\text{O}_2 < 240$;
- 2) Severe: $\text{PaO}_2/\text{F}_1\text{O}_2 \leq 100\text{mmHg}$, or $\text{SpO}_2/\text{F}_1\text{O}_2 < 140$.

COVID-19 induced adult ARDS patients admitted to the medical ICU will be enrolled when their $\text{PaO}_2/\text{F}_1\text{O}_2$ is less than 200mmHg or $\text{F}_1\text{O}_2 \geq 0.4$ is required to maintain SpO_2 at 88–93% on HFNC treatment.

2.2. Exclusion criteria

The exclusion criterion are

- 1) If the patients have a consistent $SpO_2 < 80\%$ when on evaluation with a FiO_2 of 0.6, or signs of respiratory fatigue ($RR > 40/\text{min}$, $PaCO_2 > 50\text{mmHg}$ / $pH < 7.30$, and obvious accessory respiratory muscle use);
- 2) Immediate need for intubation ($PaO_2/FiO_2 < 50\text{mmHg}$ or $SpO_2/FiO_2 < 90$, unable to protect airway or mental status change);
- 3) Hemodynamic instability (sustained $SBP < 90\text{mmHg}$, sustained MBP below 65 mmHg or requirement for vasopressor);
- 4) Unable to collaborate with HFNC/PP with agitation or refuse HFNC/PP.
- 5) Chest trauma or any contraindication for PP
- 6) Pneumothorax
- 7) Age < 18 years
- 8) Pregnant
- 9) Unable to communicate
- 10) Severe obese ($BMI \geq 40$)
- 11) Patient self-proned for more than an hour

3. PROCEDURES INVOLVED

3.1. Recruiting and consent

All patients admitted with COVID-19 will be screened and patients with ARDS who will be selected by the inclusion and exclusion criteria are included.

All participating subjects provide electronic informed consent or telephone consent before randomization.

3.2. Randomization and masking

Randomization will be stratified on ARDS severity (moderate and severe) performed by permuted block methods using Fisher and Yates tables of random permutations using a centralized interactive contact system is used for randomization. The random block length is 4, and random numbers are generated by computer. All of the centers participating in this study are immediately put in contact with the central unit (Rush University Medical Center) to obtain a randomization number if a patient fulfills the inclusion criteria. Within 6 hr of fulfilling inclusion criteria, a patient will be randomly allocated either to the prone positioning group or the control group (HFNC alone with no prone positioning therapy).

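### Randomisation is stratified by ARDS severity, but no planned comparison of the arms uses the strata; if severity predicts intubation, the tests are conservative and power is given away.

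*Combined protocol and SAP*

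**What the plan says.** Section 3.2 (Randomization and masking): "Randomization will be stratified on ARDS severity (moderate and severe) performed by permuted block methods". It adds: "The random block length is 4, and random numbers are generated by computer".

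Section 4.2 (Statistical analysis) lists the comparisons between the arms. Continuous variables get a t test or Mann-Whitney test. For binary outcomes, "Qualitative or categorical variables are compared with the chi-square test" or Fisher's exact test. For time on spontaneous breathing it uses the "Kaplan-Meier estimate of survival and the log-rank test to compare the two groups". Severity appears in none of these. The one multivariable model is a logistic regression of risk factors for failure of prone positioning, which does not compare the arms.

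Section 4.3 (Sample size calculation) works from one pooled figure, an "expected intubation rate of 60% in the moderate to severe ARDS patients with HFNC support", against 45% with prone positioning. It gives no rate or share for moderate and severe patients separately.

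Two other places bear on the strata. Section 1.1 reports from a preliminary study that "Severe ARDS patients were not appropriate candidates for HFNC/NIV+PP". Section 2.1 states: "Patients are categorized into 2 mutually exclusive classes of ARDS severity".

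**The concern.** Stratified blocks make the arms nearly equal within each severity class, so chance imbalance in severity adds almost nothing to the true variance of the treatment difference. An unstratified test still uses the total variance, including the part between strata. If severity is prognostic, the standard error is too large: the test rejects less than 5% of the time under the null and loses power under the alternative. A stratified test removes that part at no cost in patients.

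The plan also provides no treatment effect by stratum, although section 1.1 raises doubt about severe patients and section 2.1 enrols them.

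**Working it through.** **1. The plan's own figure.** Inputs from section 4.3: 60% v 45%, 80% power; from 4.2: 5% level. Two-sided testing and 1:1 allocation are assumed, since neither is stated. Pooled-variance formula, mean rate 0.525:

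n per arm = [1.960 × √(2 × 0.525 × 0.475) + 0.842 × √(0.60 × 0.40 + 0.45 × 0.55)]² / 0.15² = (1.384 + 0.588)² / 0.0225 = 172.8

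This rounds to 173 per arm, 346 in total, as stated. The trial is therefore sized for an unstratified two-proportion test. (The bracket in 4.3 prints 80% × 0.75, which is 60%; 60% × 0.75 gives the 45% used. The 346 is unaffected.)

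**2. Direction, by formula.** Take two equal strata whose control rates differ by d around a mean of 0.60. Total variance is 0.60 × 0.40 = 0.24, of which d²/4 lies between strata. The within-stratum share is s = 1 − (d²/4)/0.24. The unstratified test at nominal 5% then has a true two-sided level of about 2 × [1 − Φ(1.960/√s)].

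| Control rates | s | 1.960/√s | Approximate true level |
|---|---|---|---|
| 55/65 | 0.990 | 1.970 | 4.9% |
| 50/70 | 0.958 | 2.002 | 4.5% |
| 45/75 | 0.906 | 2.059 | 4.0% |
| 40/80 | 0.833 | 2.147 | 3.2% |

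**3. Size, by simulation, equal strata.** N = 346, blocks of 4 within stratum, overall rates 60% v 45%, no continuity correction, 200,000 trials per scenario (Monte Carlo standard error 0.1 point on power, 0.05 on type I error). Each cell gives unstratified chi-square v Cochran-Mantel-Haenszel (CMH), in %.

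| Control rates | Type I error | Power, common risk ratio 0.75 | Power, common 15-point difference | Power, common odds ratio |
|---|---|---|---|---|
| 55/65 | 4.95 v 5.07 | 79.3 v 79.6 | 79.6 v 80.0 | 79.4 v 79.9 |
| 50/70 | 4.72 v 5.11 | 79.5 v 81.1 | 79.9 v 82.0 | 79.8 v 81.9 |
| 45/75 | 4.06 v 5.01 | 80.3 v 83.2 | 80.2 v 83.6 | 80.5 v 83.9 |
| 40/80 | 3.26 v 4.98 | 81.1 v 85.3 | 81.3 v 86.6 | 81.6 v 87.0 |

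**4. Range over the unknowns.** Severe share 20%, 35% or 50%, and the three effect scales above:

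| Stratum difference in control intubation | Power gained by CMH (points) | Unstratified type I error |
|---|---|---|
| 0 | 0 | 5.0-5.2% |
| 10 | 0.3-0.5 | 5.0-5.1% |
| 20 | 1.1-2.1 | 4.6-4.8% |
| 30 | 2.2-3.4 | 4.1-4.4% |
| 40 | 3.0-5.5 | 3.3-3.9% |

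Unstratified power stays at 79-82% and CMH type I error at 4.9-5.1% throughout. Independent simulations of the binary comparison agree closely.

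**5. Log-rank.** Equal strata, constant hazards to day 28, 28-day risk ratio 0.75, 20,000 trials. Unstratified v stratified power at differences of 10, 20, 30 and 40 points: 82.5 v 82.8, 83.4 v 85.2, 83.6 v 87.4, 85.5 v 91.3%. Null rejection: 5.1 v 5.1, 4.5 v 5.1, 3.9 v 5.1, 3.3 v 5.2%. The t, Mann-Whitney and Fisher tests were not simulated; the argument in step 2 applies to them in direction only.

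**6. Effects by stratum.** Equal strata, control rates 50/70, about 86.5 patients per arm per stratum. With reductions of 20 and 10 points (50 to 30, 70 to 60), the standard error of the difference between strata is √[(0.25 + 0.21 + 0.21 + 0.24)/86.5] = 0.103. A 10-point interaction is thus about one standard error. Simulated power is 17%, and 32% for reductions of 22.5 v 7.5 points. Stratum results can only be descriptive.

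**7. The classes themselves (separate, minor).** In section 2.1 a PaO2/FiO2 of exactly 100 meets both definitions, and one patient's PaO2/FiO2 and SpO2/FiO2 may point to different classes. Section 1.4 lets SpO2/FiO2 stand in for PaO2/FiO2, but "as a means for evaluating oxygenation" under secondary outcomes, not as a rule for the randomisation stratum. This does not cause the conservatism and does not affect which arm a patient receives.

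**The case against.** The strongest reply is that the plan delivers what it promises. It was sized for an unstratified test, keeps its 80% power, and errs on the safe side under the null. The documents give no rate by stratum, so the larger losses depend on differences nobody has shown; 40 points means control rates such as 40% v 80%, or 52% v 92% when 20% are severe. Section 2.2 excludes the sickest patients, which truncates the severe class. With only 10% severe, the chi-square loss is about 0.3, 0.6 and 1.6 points at differences of 10, 20 and 30. At a 10-point difference the simulated level shows no detectable conservatism.

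All of this is right, and it limits the size and rank of the point. It does not remove the mismatch: nothing elsewhere in the documents brings severity into a comparison of the arms. The sponsor chose severity as its only stratification factor, which suggests it is expected to matter. If it does not, the stratified test costs nothing (79.3% v 79.3%).

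Two further objections stand in part. Section 1.1 ends by calling for study of moderate to severe ARDS, so enrolling severe patients is deliberate; that supports showing their result but does not make a formal subgroup test worthwhile. And section 4.1 does not list the stratum among the collected data, so its availability is inferred from section 3.2.

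**Conclusion.** The concern holds. The analysis ignores the factor on which randomisation is stratified. If severity predicts intubation, the unstratified tests are conservative and forgo power. The likely loss for the binary comparison is modest: 0-2 points for stratum differences up to 20 points, and about 2-5.5 points at 30-40. The log-rank loss is somewhat larger at the upper end (about 3.8 points at 30 and 5.8 at 40, equal strata).

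These figures assume 1:1 allocation, overall rates of 60% v 45%, a severe share of 20-50% for the binary test, and a constant effect across strata on one scale. The validity of the trial and its stated power are not in question. The change should be made because it is free, but the trial does not fail without it.

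**What to change.** In section 4.2:

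- Make the primary binary comparison a CMH test stratified by severity as recorded at randomisation, and name in advance a stratum-adjusted risk difference or risk ratio, so the effect stays on the scale of section 4.3.
- Use a severity-stratified log-rank test.
- Adjust oxygenation comparisons for baseline SpO2/FiO2 and severity.
- Report the effect by stratum with confidence intervals, labelled descriptive.

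In section 2.1, assign the value 100 to one class only and state which ratio decides the randomisation stratum when both are available. In section 4.1, list the randomisation stratum among the data collected.

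The cost is wording, settled before database lock. No patients are added, and the stratum must already be known in order to randomise.

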3.3. Blinding and Quality Control

The trial will be overseen by a steering committee, and data quality control will be completed by independent data monitoring board. Clinicians and epidemiologists of above organization are not members of participating in our research group. Research coordinator will timely verify database and regularly monitored all the centers on site to ensure the accuracy of

the data recorded. An investigator at each center is responsible for enrolling patients in the study, ensuring adherence to the protocol, and completing the electronic case-report form. Although the individual study assignments of the patients could not be blinded, the coordinating center and all the investigators will remain unaware of the study group outcomes until the data are unlocked. All the analyses are performed by the study statistician not involved in study recruitment, and blind of randomization group until database lock.

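### The single block length of 4 is printed in the protocol of an open-label trial; varying it at random would cheaply remove most certain foreknowledge of allocation, a risk that central randomisation already limits

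*Combined protocol and SAP*

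**What the plan says.** Section 3.2 (Randomization and masking) describes the method: "Randomization will be stratified on ARDS severity (moderate and severe) performed by permuted block methods". Severity is the only stratification factor named, so two lists are implied. On block size it says: "The random block length is 4, and random numbers are generated by computer". The word random stands before block length, but only one value follows, so as written the length is constant.

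Allocation is central: "All of the centers participating in this study are immediately put in contact with the central unit". The time allowed is up to six hours: "Within 6 hr of fulfilling inclusion criteria, a patient will be randomly allocated". There are two arms, prone positioning and control, and the allocation ratio is not stated.

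Section 3.3 (Blinding and Quality Control) concedes: "Although the individual study assignments of the patients could not be blinded". The masking described there covers group outcomes and the statistician, not the assignments seen at the bedside. It also says who recruits: "An investigator at each center is responsible for enrolling patients in the study". Among the exclusions in section 2.2, one calls for judgement about the patient in front of the investigator: "Unable to collaborate with HFNC/PP with agitation or refuse HFNC/PP".

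Neither section says that the block length is kept from the people who enrol.

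**The concern.** When treatment is visible and the block length is known and constant, past assignments carry information about the next one. Someone who can foresee the arm, and who has discretion over whether or when a patient enters, can let the one influence the other. The documents leave some room for this: there is up to six hours between eligibility and allocation, and one exclusion turns on whether the patient can cooperate with prone positioning. A patient thought unlikely to tolerate proning could be judged ineligible when the prone arm is expected and eligible when control is expected. The arms would then differ in prognosis at entry, and an intention-to-treat comparison would not correct that.

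**Working it through.** **The plan's own figure, and the allocation ratio.** The documents give no predictability figure. The ratio has to be assumed, and section 4.3 helps. With 60% against 45%, two-sided alpha 0.05, power 80% and equal arms:

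n per arm = [1.960·√(2·0.525·0.475) + 0.842·√(0.60·0.40 + 0.45·0.55)]² / 0.15² = (1.384 + 0.588)² / 0.0225 ≈ 172.8, rounded up to 173.

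The total is 2 × 173 = 346, as stated, so 1:1 is a supported assumption. (The bracket in section 4.3 prints 80% × 0.75, which is 60%; it is 60% × 0.75 = 45% that reproduces the total. That is a separate matter.)

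**Full view of one stratum, fixed block of 4.** There are six equally likely orders of two and two.
- Certain allocations: the fourth is always determined, and the third is determined when the first two match, which has probability 1/3. Expected number per block: 1 + 1/3 = 4/3. Share: (4/3)/4 = 33.3% (8 of 24 positions). If both strata were fully visible, that is about 346/3 ≈ 115 patients.
- Best guess: success by position is 1/2, 2/3, 2/3 and 1. The mean is (17/6)/4 = 17/24 = 70.8%, against 50% without blocking.

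**Partial view.** Suppose a site supplies a share s of a stratum, its patients fall at random among those of other sites, and (generously) it knows where each block starts.
- Third position certain: both earlier patients seen and alike, s²/3.
- Fourth position certain: both members of the matching pair seen, s².
- Share certain: (s²/3 + s²)/4 = s²/3.

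A simpler rule, guessing the opposite of the site's own last patient, needs no knowledge of block position. Two patients in the same block of 4 differ with probability 2/3, an excess of 1/6 over one half. Two patients k places apart share a block with probability (4 − k)/4, for k = 1 to 3. So accuracy = 1/2 + (1/6)·Σ s(1 − s)^(k−1)·(4 − k)/4.

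| Share s | Certain, s²/3 | Opposite-of-last guess correct |
|---|---|---|
| 1/2 | 8.3% | 1/2 + 0.531/6 = 58.9% |
| 1/3 | 3.7% | 1/2 + 0.398/6 = 56.6% |
| 1/4 | 2.1% | 1/2 + 0.316/6 = 55.3% |

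**Lengths 4, 6 and 8 chosen at random with equal probability.**
- Full view, observer knowing the set of lengths but not the current one (simulation, 300 runs of 173 patients): about 2% certain and 68% best-guess accuracy. With lengths 4 and 6 only: about 5% and 69%.
- Half-share opposite-of-last guess: for length b the excess is 1/[2(b − 1)], and b − k pairs lie k places apart in each block. Summing over k with s = 1/2 gives 2.125/6 + 4.031/10 + 6.008/14 = 1.186 per 4 + 6 + 8 = 18 patients. Accuracy = 1/2 + 1.186/18 = 56.6%.
- Maximum imbalance in a stratum is half the largest block: 8/2 = 4, against 4/2 = 2 now.

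**The case against.** The strongest reply is that the plan already has the main safeguard. Sites must contact a central unit for each assignment, and centre is not a named stratum, so an investigator at one of several sites sees only fragments of a sequence. That stands. It makes one third a ceiling that applies only to someone with the whole sequence, and the certain share falls with the square of a site's share.

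A reader might infer that site staff in general can foresee a third of allocations, or that one site will dominate the severe stratum. The documents support neither: they give no number of sites, no recruitment shares and no split between moderate and severe. The central unit's staff may see every assignment, but enrolment is given to an investigator at each centre, and nothing says that the same people do both.

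Opportunity is also limited. Six hours is a maximum, centres are to make contact at once, all admitted COVID-19 patients are screened (section 3.1), and most exclusions are numeric or factual. Concealment is therefore not the only protection.

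Finally, the remedy does little against guessing: for a half-share site the gain is about two percentage points. That stands too. The clear gain is the removal of near-certainty for anyone with a full view.

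What the reply does not dispose of is that the length is constant, is printed in the protocol investigators follow, and is not withheld from them. How well concealment holds depends on site shares and central-unit roles that the documents do not describe.

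**Conclusion.** The point holds as a cheap improvement of low severity. Under 1:1 allocation, foreknowledge with a full view of a stratum is 33% certain and 71% by best guess. For a site with half of a stratum it is at most about 8% certain, or 59% by the simple guess. The site figures assume that patients from different sites arrive in random order; long runs from one site would raise them towards the full-view figures, and the documents do not show how recruitment falls.

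A reader might go further and conclude that selection bias has occurred or that concealment has failed. The documents show a route by which bias could arise, not that anyone used it. Nor do they show when sites could first read the block length, only that the protocol prints it.

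**What to change.** Have the central system draw block lengths at random, for example from 4, 6 and 8. Say in the protocol only that lengths vary, and keep the values in a restricted randomisation document that sites do not receive. It would also help to state whether central-unit staff who can see the sequence take part in screening or enrolment.

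The cost is a setting in the randomisation program and the larger maximum imbalance per stratum shown above. The sample size does not change. If enrolment is already complete, report the block length and each site's share of each stratum so that readers can judge the exposure.
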